4.2 Scientific Rationale for the Study Design

4.2.1 Rationale for Study Population

HZNP-DAX-204 is a Phase 2 OLE study to evaluate the long-term safety and tolerability of daxdilimab in subjects with SLE. Subjects who complete the 48-week treatment period of the RECAST SLE study will be eligible to enroll in the SLE OLE study; therefore, the baseline characteristics of the study population in the SLE OLE study will be similar to that of the RECAST SLE study.

To evaluate the long-term safety and tolerability of daxdilimab in the SLE OLE study, only subjects who complete the 48-week treatment period of the RECAST SLE study and meet the eligibility criteria for the OLE will be eligible to participate in the clinical study. The selection criteria will allow for the assessment of long-term safety and tolerability of daxdilimab in subjects with SLE, while addressing safety concerns. This approach is justified by the favorable safety and tolerability profile observed in nonclinical ([Section 2.2.4](#)) and emerging clinical ([Section 2.2.5](#)) safety data from completed and ongoing clinical studies with daxdilimab.

The study population in the SLE OLE study reflects a subpopulation of patients who would be considered suitable for the therapy if daxdilimab is shown to be safe and effective.

4.2.2 Rationale for the Primary Outcome Measure

The safety endpoints are incidence of AEs, SAEs, and AESIs, which are standard assessments to evaluate safety and tolerability.

4.2.3 Rationale for the Secondary Outcome Measure

Pharmacokinetic sampling is included to evaluate subjects' exposure to multiple doses of daxdilimab administered SC. Pharmacodynamic assessments, [REDACTED]

General risks of biologic therapies include development of anti-drug antibodies (ADAs). Because ADAs to daxdilimab could result in altered daxdilimab levels or activity, ADA rate and the effect of ADA in the PK profile of daxdilimab will also be evaluated.

4.3 Rationale for Dose

A 200 mg daxdilimab dose administered Q12W has been selected to evaluate whether this decreased frequency of daxdilimab dosing can maintain clinical efficacy and to reduce the risk of safety and tolerability findings in the long term.

Treatment with daxdilimab in a single-blind, Phase 1b MAD study, resulted in a favorable safety profile and rapid and durable depletion of blood pDCs in all subjects receiving a 150 mg Q4W dose. Depletion of blood pDCs remained decreased until 3 months after the final dose when 90% of subjects recovered to within at least 50% of baseline. The 200 mg Q12W dosing strategy will allow for the evaluation of whether blood pDC depletion and recovery reaches a steady state and can be maintained by less frequent dosing.

A treatment period of 48 weeks is considered sufficient to evaluate long-term safety of daxdilimab and the secondary PK/PD outcome measures selected for this OLE study, and current nonclinical ([Section 2.2.4](#)) safety data supports this treatment duration.

4.4 End-of-Study Definition

An individual subject will be considered to have completed the study if the subject was followed up through the last protocol-specified visit, regardless of the number of doses of IP that was received.

Subjects will be considered not to have completed the study if consent was withdrawn ([Section 7.2](#)) or the subject was lost to follow-up ([Section 7.3](#)).

The end of the study (“study completion”) is defined as the date of the last protocol-specified visit/assessment for the last subject in the study.

Information regarding site/study termination or suspension is found in Appendix 1, [Section 10.1.12](#).

5 STUDY POPULATION

5.1 Inclusion Criteria

All subjects must meet all of the following criteria to be eligible for study participation:

1. Willing and able to understand and provide written informed consent (as described in Appendix 1, [Section 10.1.3](#)) prior to any study-related procedures and to comply with all study requirements and complete study assessments.
2. Must have qualified for and received IP (daxdilimab or placebo) and complete the treatment period (through Day 337) in the RECAST SLE study. Subjects who discontinued early from IP in RECAST SLE are not eligible for this study.
3. Women of childbearing potential must have a negative urine pregnancy test on Day 1. Women of childbearing potential are defined as those who are not surgically sterile (ie, surgical sterilization includes bilateral salpingectomy, bilateral oophorectomy, or hysterectomy) or those who are not postmenopausal (defined as 12 months with no menses without an alternative medical cause and a follicle-stimulating hormone [FSH] within the postmenopausal range as established by the central laboratory during the

screening period of the RECAST SLE study, unless on postmenopausal hormone replacement therapy).

If a female subject becomes postmenopausal during the study (ie, 12 months with no menses without an alternative medical cause, unless on postmenopausal hormone replacement therapy), a FSH test will be performed at the central laboratory. If the FSH level is within the postmenopausal range, the female subject will not be required to use contraception after that.

Women of childbearing potential who are sexually active with a nonsterilized male partner must agree to use a highly effective method of contraception from signing of the ICF and must agree to continue using such precautions through the end of the study follow-up or 3 months (approximately 5 half-lives) following the last dose of IP in the case of early withdrawal from the study, and refrain from egg retrieval/egg donation during this period. After this point, a decision about contraception should be made by the subject and her regular healthcare providers. Female subjects who participate in the SLE OLE are expected to maintain the same form of contraception they used during the RECAST SLE study. Effective methods of contraception are listed in Appendix 3, [Section 10.3](#).

Sustained abstinence is an acceptable practice; however, periodic abstinence, the rhythm method, and the withdrawal method are not acceptable methods of contraception.

Note that because mycophenolate affects the metabolism of hormonal contraceptives and may reduce their effectiveness in women receiving MMF or mycophenolic acid (MPA) who are using hormonal contraceptives for birth control, the subject must employ an additional contraceptive method (eg, barrier method).

4. Nonsterilized male subjects who are sexually active with a woman partner of childbearing potential must agree to use a condom with spermicide from Day 1 and until 3 months (approximately 5 half-lives) after receipt of the last dose. Because a male condom with spermicide is not a highly effective contraception method, it is strongly recommended that male subjects advise their women partners of childbearing potential to use a highly effective method of contraception throughout this period. Effective methods of contraception are listed in Appendix 3, [Section 10.3](#).

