Note: *Enrolled* means subjects, 'or their legally acceptable representatives', agreement to participate in a clinical study following completion of the informed consent process and eligibility review. Potential subjects who are screened for the purpose of determining eligibility for the study, but do not participate in the study, are not considered enrolled, unless otherwise specified by the protocol. A subject will be considered enrolled if the informed consent is not withdrawn prior to participating in any study activity after eligibility review.

Intervention Groups and Duration

Subjects will receive 200 mg daxdilimab Q12W for 48 weeks (Weeks 0 [Day 1], 12, 24, 36, and 48). Following the final dose administration at Week 48, subjects will be followed up for an additional 8 weeks for a total study duration of approximately 56 weeks.

Investigational Product: Dosage and Mode of Administration

The investigational product (IP) is daxdilimab. Daxdilimab will be provided as a sterile liquid in a 2R glass vial with a nominal 1.0 mL of 100 mg/mL daxdilimab. Daxdilimab drug product is stored at 2°C to 8°C in a refrigerator with adequate temperature monitoring in a location with limited access.

Daxdilimab is to be administered as two 1.0-mL SC injections.

Visit Frequency

The study will be conducted on an outpatient basis. For scheduled study visits, subjects will come to the study sites on 7 occasions: Weeks 0 [Day 1], 12, 24, 36, 48, 52, and 56. For all IP administrations, daxdilimab will be administered by study-site staff at the study site. Subjects will also attend telehealth visits (phone or video call) on 8 occasions: Weeks 4, 8, 16, 20, 28, 32, 40, and 44.

- Study duration: approximately 56 weeks
- Treatment duration and frequency: 48 weeks with in-clinic visits Q12W and telehealth visits Q4W between in-clinic visits
- Follow-up duration and frequency: 8 weeks with 2 visits 4 weeks apart

[figure not shown]
Data Monitoring/Other Committee:

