4 STUDY DESIGN

4.1 Overall Design

Protocol HZN-DAX-204 is an open-label study designed to evaluate the long-term safety and tolerability of 200 mg daxdilimab Q12W in subjects with SLE. The study design is provided in [Section 1.2 \(Figure 1\)](#).

Irrespective of their assigned treatment in the RECAST SLE study, all subjects participating in the SLE OLE will be treated with daxdilimab 200 mg SC Q12W in addition to their standard-of-care SLE therapy.

Once a subject has completed the treatment period (through Week 48) of the RECAST SLE study, signed the informed consent form (ICF), and met all study eligibility criteria, he/she may be enrolled in the OLE study. To allow for the continuous dosing of the subjects, the start of this OLE study should occur immediately after the completion of the RECAST SLE treatment period (ie, first OLE dosing [Day 1] coinciding with Week 48/Visit 14 of the RECAST SLE study). Any exceptions to this enrollment date must be reviewed and approved by the Medical Monitor before any subject is allowed to enroll after the Week 48/Visit 14 of the RECAST SLE study. ([Section 5.5](#)). Subjects will be treated with open-label daxdilimab 200 mg Q12W SC for 48 weeks. After the treatment period (Week 0 to Week 48), the subjects will enter an 8-week safety follow-up (SFU) period (Week 48 to Week 56).

Subjects who permanently discontinue IP at any point but who **do not** withdraw consent of study participation will complete the Study Week 48/early termination (ET) visit as soon as possible after IP discontinuation and then enter the SFU period as indicated in the schedule of assessments (SoA) ([Table 1](#)). Participants will not automatically be removed from the study if any administration of IP is missed.

The study will be conducted on an outpatient basis. For scheduled study visits, subjects will come to the study sites on 7 occasions: Weeks 0 [Day 1], 12, 24, 36, 48, 52, and 56. In addition, telehealth visits (phone or video call) will be performed on 8 occasions (Weeks 4, 8, 16, 20, 28, 32, 40, and 44) to assess the subject's current disease status, the OGC tapering schedule, safety, and concomitant medications ([Section 8.1](#)). For all IP administrations, daxdilimab will be

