7.1 Discontinuation of Investigational Product

An individual subject will not receive any further IP if any of the following occur in the subject:

- Receipt of any medications or therapies in [Section 6.9.3](#).
- A Grade 3 or higher allergic reaction to the IP.
- A Grade 3 or higher infection considered related to the IP.
- Other AE that contraindicates further dosing in the opinion of the Investigator and/or the Sponsor, Medical Monitor, and/or the SDMC.
- Withdrawal of consent from further treatment with IP.
- Subject is determined to have met one or more of the exclusion criteria or failed to meet all the inclusion criteria for study participation and there is a potential safety risk associated with continuation identified upon consultation with the Medical Monitor.
- Pregnancy or a decision to become pregnant.
- Any of the following liver function abnormalities:
 - Alanine aminotransferase (ALT) or aspartate aminotransferase (AST) $\geq 8 \times$ upper limit of normal (ULN).
 - ALT or AST $\geq 5 \times$ ULN for more than 2 weeks.
 - ALT or AST $\geq 3 \times$ ULN and total bilirubin $\geq 2 \times$ ULN or international normalized ratio ≥ 1.5 without alternative explanation.
 - ALT or AST $\geq 3 \times$ ULN with the appearance of fatigue, nausea, vomiting, right upper quadrant pain or tenderness, fever, rash, and/or eosinophilia ($\geq 5\%$).

Subjects who permanently discontinue IP at any point but who **do not** withdraw consent of study participation will complete the Study Week 48/ET visit as soon as possible after IP discontinuation and then enter SFU period unless the subject withdraws consent of study participation (as described in Section 7.2) or the subject is lost to follow-up (Section 7.3).

Appendix 4, [Section 10.4](#) describes the process to be followed to identify and appropriately report potential Hy's Law cases and Hy's Law cases.

Follow the SoA ([Table 1](#)) for data to be collected at the time of discontinuation of IP and follow-up and for any further evaluations that need to be completed.

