8.4.8 Pregnancy

Pregnancy in a woman who has received IP must be reported to the Sponsor from time of signed ICF until end-of-study follow-up or 3 months (approximately 5 half-lives) following the last dose of IP in case of early withdrawal. The Investigator must report the pregnancy to the Sponsor or representative as if it were an SAE (ie, within 24 hours of learning of the pregnancy) Refer to [Section 8.4.7](#) for additional information.

Subjects who become pregnant during the study period must not receive additional doses of IP. These subjects will discontinue IP and follow the IP discontinuation procedures ([Section 7.1](#)). While pregnancy itself is not considered to be an AE or SAE, any pregnancy complication or elective termination of a pregnancy for medical reasons will be reported as an AE or SAE.

Abnormal pregnancy outcomes (eg, spontaneous abortion, fetal death, stillbirth, congenital anomalies, ectopic pregnancy) are considered SAEs and will be reported as such.

The subject will be followed to determine the outcome of the pregnancy. The Investigator will collect follow-up information on the subject and the neonate, and the information will be forwarded to the Sponsor after the outcome.

Should the Investigator become aware of a pregnancy in the partner of a male study subject who has received IP, this should be reported to the Sponsor within 24 hours of knowledge of the event (refer to [Section 8.4.7](#) for additional information). The Sponsor will endeavor to collect follow-up information on such pregnancies, provided the partner of the study subject provides consent for disclosure of their information.

Any poststudy pregnancy-related SAE considered reasonably related to the IP by the Investigator will be reported to the Sponsor as described in [Section 8.4.7](#). While the Investigator is not obligated to actively seek this information in former study subjects or pregnant female partner, he or she may learn of an SAE through spontaneous reporting.

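### Women who take the Week 48 dose and complete the study are released from required contraception about 8 weeks later, roughly 4 to 5 weeks short of the protocol's own 3-month post-dose period

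*Protocol*

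**What the plan says.** Criterion 3 in Protocol section 5.1 sets the contraception period for women of childbearing potential who are sexually active with a nonsterilized male partner. It starts at consent, and its endpoint is given as "end of the study follow-up or 3 months (approximately 5 half-lives) following the last dose of IP in the case of early withdrawal". The withdrawal meant in that criterion is withdrawal from the study. Egg retrieval and donation are barred for the same period. Afterwards the decision passes to the woman and her own healthcare providers.

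Section 8.4.8 has the same structure for pregnancy reporting, which runs "until end-of-study follow-up or 3 months (approximately 5 half-lives) following the last dose of IP in case of early withdrawal".

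Criterion 4 requires contraception from nonsterilized men with a partner of childbearing potential until 3 months after the last dose. It equates that with about 5 half-lives, as criterion 3 does, but does not make it depend on early withdrawal.

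The last planned dose is at Week 48. The Synopsis states: "Following the final dose administration at Week 48, subjects will be followed up for an additional 8 weeks". It lists the follow-up as "Follow-up duration and frequency: 8 weeks with 2 visits 4 weeks apart".

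Subjects who permanently stop investigational product (IP) without withdrawing consent have the early termination (ET) assessments, shared with Week 48, at a "visit as soon as possible after IP discontinuation and then enter the SFU period as indicated in the schedule of assessments" (section 4.1; section 7.1 is similar).

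**The concern.** The protocol names one post-dose period, 3 months or about 5 half-lives, and applies it to men generally but to women only on early withdrawal. The planned path includes a dose at Week 48 and a final visit 8 weeks later. A woman who takes every dose and completes therefore has a shorter required period after her last dose than the one set for a woman who withdraws. Neither document explains the difference.

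At stake is a reproductive-safety precaution. The requirement and the egg retrieval and donation restriction both end before the protocol's own period has passed. Routine pregnancy reporting under section 8.4.8 ends at the same point. After that, only pregnancy-related SAEs that the investigator learns of and considers related to IP are reportable (sections 8.4.4 and 8.4.8). Section 2.2.1 notes that SLE is about nine times as common in women as in men and that onset in women is typically in the childbearing years, so this is a core part of the population. The number of women affected is not given.

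**Working it through.** **Inputs.** Week 48 is Day 337 and Week 56 is Day 393, each ±7 days (Table 1, section 1.3). The period of 3 months, about 5 half-lives, comes from criteria 3 and 4. Its length in days is not stated, so I take 84 days (12 weeks) and 91 days as assumptions.

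**The plan's own figure.** 393 − 337 = 56 days = 8 weeks, matching the stated follow-up.

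**Completer dosed at Week 48, counting to her own last visit.**
- Nominal shortfall: 84 − 56 = 28 days, or 91 − 56 = 35 days.
- Windows: the dose falls on Days 330 to 344 and the last visit on Days 386 to 400. Shortest interval 386 − 344 = 42 days; longest 400 − 330 = 70 days.
- Shortfall at 84 days: 84 − 70 = 14 to 84 − 42 = 42 days.
- Shortfall at 91 days: 91 − 70 = 21 to 91 − 42 = 49 days.
- No in-window schedule reaches 3 months on either definition.

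**Scale in half-lives (illustration only, assuming first-order elimination).** The implied half-life is 84/5 = 16.8 days or 91/5 = 18.2 days. At 56 days, 56/16.8 = 3.3 or 56/18.2 = 3.1 half-lives have passed. The fraction remaining is 2^(−3.33) = 9.9% or 2^(−3.08) = 11.8%, against 2^(−5) = 3.1% at 5 half-lives. The point does not depend on this.

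**Trial-wide reading.** Section 4.4 defines the end of the study as "the date of the last protocol-specified visit/assessment for the last subject in the study". If criterion 3 means that date, a woman finishing x days before it is covered for 56 + x days. She is short only if x is below 35 (91-day definition) or 28 (84-day definition). The last women to finish are still released at about 56 days.

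**Permanent discontinuation of IP, staying in the study.** Suppose the 8-week follow-up is counted from the ET visit, d days after her last dose. Follow-up then ends at d + 56 days, and she is nominally short if d is below 35 (91 days) or 28 (84 days). For example, d = 7 gives 63 days, 28 short of 91. If she stops when the next dose is due, d = 84 gives 140 days and no shortfall. If instead the calendar visits in Table 1 apply, a woman whose last dose was at Week 36 is followed for 56 − 36 = 20 weeks and is not short. The same holds for a woman who only misses the Week 48 dose and stays on schedule.

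**The case against.** **The key phrase is undefined.** On the trial-wide reading, women who finish at least about 5 weeks before the last subject already have 3 months. This stands as a limit on how many women are affected. It does not remove the gap, because late finishers are still short, and a woman's obligation would then depend on when someone else finishes.

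**Early discontinuation.** A reader might infer that every woman who stops IP early but stays in the study is also short. The documents do not support that. They do not say whether the follow-up clock restarts at the ET visit: section 4.1 points to a schedule that lists only Days 365 and 393, and section 7.3 judges loss to follow-up by status on Day 393. They do not define early withdrawal either. Section 4.4 says "Subjects will be considered not to have completed the study if consent was withdrawn", with loss to follow-up as the other route, but that defines non-completion. Section 8.4.8 omits the words tying withdrawal to the study, and section 6.9.1.2.1 speaks of withdrawal from the IP. A site could reasonably apply the 3-month rule to these women. This objection stands, so that group is a conditional case only.

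**Limited consequence.** Urine pregnancy tests are scheduled at Weeks 48, 52 and 56, the woman's own providers take over afterwards, and related post-study pregnancy SAEs that come to light remain reportable. The 6-month monkey study reported no effects on reproductive organs or assessments (section 2.2.4), though that is not embryo-fetal evidence. All of this is fair. It does not explain why the protocol sets 3 months for men and for women who withdraw but not for women who complete. The Investigator's Brochure and consent form might address the period; they are not available here.

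**Conclusion.** The concern holds for women dosed at Week 48 who complete. With the period counted to the woman's own last visit, required contraception ends 56 days after the last dose (42 to 70 with windows). That is about 4 to 5 weeks short of 3 months, or 14 to 49 days across windows and both day counts, and no reason is stated. On the trial-wide reading the shortfall is confined to women finishing within about 5 weeks of the last subject's last visit.

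Women who permanently stop IP and stay in the study may also be short, but only if three things hold together: follow-up is counted from the ET visit, they are not treated as early withdrawals, and ET falls within about 5 weeks of the last dose.

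Two further inferences go beyond the documents. One is that the shorter period causes fetal harm: no such evidence is given, and the yardstick here is only the protocol's own period. The other is that pregnancies are better captured after withdrawal: section 7.2 stops visits and data collection then, so the firm contrast is the contraception commitment. The primary endpoint and the analyses are unaffected. This is a wording correction to a safety precaution, worth making because it is cheap. If the shorter period is deliberate, the protocol should say why.

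**What to change.** In criterion 3 and section 8.4.8, make the period run through the subject's own last study visit or 3 months (about 5 half-lives) after her last dose of IP, whichever is later, regardless of completion or discontinuation status. Naming her own last visit matters: adding only a later-of rule to the present undefined phrase could, on the trial-wide reading, bind early finishers until the last subject's last visit. Put matching wording in the consent form.

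Ask subjects to report to the site any pregnancy in that period. Pregnancies are already reported as if they were SAEs, so the existing route serves, including the paper form in section 10.2.4 if the electronic tool is offline.

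The cost is a protocol amendment in two sections with IRB/IEC approval (section 10.1.1), reconsent of women still participating (section 10.1.3), and about 5 more weeks of contraception for affected women. No visit or call is added, so the 56-week schedule, the completion definition in section 4.4 and the final-analysis trigger in SAP section 3.1 are unchanged.
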